4. STUDY OBJECTIVES AND ENDPOINTS

4.1. Study Objectives

The objective of this first-in-human study is to assess the feasibility and preliminary safety of the Endogenex device for endoscopic duodenal cellular regeneration in individuals with type 2 diabetes inadequately controlled on glucose-lowering medications.

The study will also assess, treatment efficacy, evaluated by changes in glycemic control and liver enzymes following the study index procedure.

The primary objective of the study is to assess the safety of the Endogenex device.

The 3 secondary objectives, in order of presentation are as follows:

- To assess the technical feasibility of the Endogenex device for duodenal cellular regeneration
- To assess changes in glycemic control following the procedure
- To assess changes in liver enzymes following the procedure

(Ref. Section 3.0 of the study protocol)

4.2. Endpoints

There is a single primary endpoint predicated on safety and 18 secondary endpoints. The primary safety endpoint is the proportion of patients experiencing device-related or procedure-related serious adverse events within 12 weeks of the procedure.

For a complete presentation of safety, a tabulation of all adverse events over the course of the clinical investigation will be presented. Adverse events will be summarized as follows:

- All adverse events
- All procedure-related adverse events
- All device-related adverse events
- All serious adverse events
- All serious procedure-related adverse events
- All serious device-related adverse events
- All Unanticipated Adverse Device Effects (UADE)
- All Unanticipated Serious Adverse Device Effects (USADE)

The following elements (variable – label) will be presented in the supportive data listing (Ref. Case Report Form)

AESEV - Severity

- Mild
- Moderate

- Severe

AEOUT - Outcome

- Ongoing
- Resolved
- Resolved with sequela
- Stabilized
- Death
- Unknown

AEDREL - Relationship to Device

- Definitely related
- Possibly related
- Unlikely related

Not Related**AEPREL - Relationship to Procedure**

- Definitely related
- Possibly related
- Unlikely related
- Not Related

AESER - Is this event a Serious Adverse Event?

- Yes
- No

AESDTH - Led to death?

- Yes
- No

AESHOSP - Resulted in hospitalization (hospital stay >24 hours) or prolongation of an existing hospitalization?

- Yes
- No

AESLIFE - Led to life threatening illness or injury?

- Yes
- No

AESMIE - Required intervention to prevent life-threatening illness or injury or permanent impairment of a body structure or body function?

- Yes
- No

AESDISAB - Resulted in permanent impairment of a body structure or body function?

- Yes

- No

AESCONG - Led to fetal distress, fetal death or a congenital abnormality or birth defect?

- Yes
- No

AEUADE - Is this event considered by the investigator to be an UADE/USADE?

- Yes
- No

4.2.1. Secondary Endpoints

First Secondary Endpoint: Procedure success: defined as successful treatment of at least 6 cm of duodenum segment.

Second Secondary Endpoint: Procedure time: defined as the time between the Endogenex catheter insertion and the catheter removal.

Third Secondary Endpoint: Change from baseline (post-baseline minus baseline) in HbA1c reported for each pre-specified study visit.

Note: The estimates will be derived using a mixed model repeated measure procedure; the 24 week result will be the principal time point of interest.

Fourth Secondary Endpoint: Change from baseline (post-baseline minus baseline) in Fasting plasma glucose (FPG) reported for each pre-specified study visit.

Note: The estimates will be derived using a mixed model repeated measure procedure; the 24 week result will be the principal time point of interest.

Fifth Secondary Endpoint: Change from baseline (post-baseline minus baseline) in Insulin-resistance by HOMA-IR reported for each pre-specified study visit.

Note: The estimates will be derived using a mixed model repeated measure procedure; the 24 week result will be the principal time point of interest.

Sixth Secondary Endpoint Part 6a: Change from baseline (post-baseline minus baseline) in Post-prandial plasma glucose (PPG) based on mixed meal tolerance test (MMTT) reported for each pre-specified study visit.

Note: The estimates will be derived using a mixed model repeated measure procedure; the 12 week result will be the principal time point of interest.

Sixth Secondary Endpoint Part 6b: Change from baseline (post-baseline minus baseline) in beta cell function based on mixed meal tolerance test (MMTT) reported for each pre-specified study visit.

Note: The estimates will be derived using a mixed model repeated measure procedure; the 12 week result will be the principal time point of interest.

Sixth Secondary Endpoint Part 6c: Change from baseline (post-baseline minus baseline) in the disposition index based on mixed meal tolerance test (MMTT) reported for each pre-specified study visit.

Note: The estimates will be derived using a mixed model repeated measure procedure; the 12 week result will be the principal time point of interest.

Seventh Secondary Endpoint: o Time in range, glucose variability by continuous glucose monitoring (CGM)

Eighth Secondary Endpoint: Proportion of treated patients with an HbA1c improvement of $\geq 0.5\%$ points from baseline at 24 weeks (24 week value minus the baseline value).

Ninth Secondary Endpoint: Proportion of treated participants with an HbA1c improvement of ≥ 0.5 points or more at 24 weeks from baseline and maintained at 48 weeks.

Note: Proportion of treated patients who achieve a HbA1c improvement of $\geq 0.3\%$ or more at 24 weeks from baseline and maintained at 48 weeks. Patients who fail to maintain HbA1c improvement $\geq 0.5\%$ at 48 weeks, for any reason, will be counted as not having achieved this endpoint. Patients who fail to achieve a HbA1c $\geq 0.5\%$ improvement at 24 weeks will be excluded from the tabulation.

Tenth Secondary Endpoint: Change in weight from baseline (post-baseline minus baseline) by visit. Weight change will be reported in both kilograms and %TBWL.

Eleventh Secondary Endpoint: Change in glucose-lowering medication usage.

Twelfth Secondary Endpoint: Change in liver enzyme from baseline at 24 weeks (post-baseline minus baseline) for Alanine Aminotransferase (ALT).

Thirteenth Secondary Endpoint: Change in liver enzyme from baseline at 24 weeks (post-baseline minus baseline) for Aspartate Aminotransferase (AST).

Fourteenth Secondary Endpoint: Change from baseline in blood pressure by visit (systolic and diastolic run separately).

Fifteenth Secondary Endpoint: Change in lipid profile from baseline by visit: total cholesterol

Sixteenth Secondary Endpoint: Change in lipid profile from baseline by visit: triglycerides

Seventeenth Secondary Endpoint: Change in lipid profile from baseline by visit: HDL

Eighteenth Secondary Endpoint: Change in lipid profile from baseline by visit: LDL

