Intent-to-Treat: The Intent-to-Treat population includes all enrolled patients, regardless of the patient having received the target treatment (at least 6cm of duodenum treated). The point of enrollment occurs when a patient has provided written informed consent and an energy delivery has been attempted during the index procedure.

Full Analysis Set: The FAS population consists of the ITT population patients who received the target treatment (at least 6 cm of duodenum treatment) and that have at least one post-treatment follow-up examination.

Per-Protocol: The Per-Protocol population is a subset of the FAS population and includes all patients who received the target treatment, do not have any major eligibility violations, and maintained stable glucose-lowering medications for 24 weeks post-procedure. The definition of what constitutes a major eligibility violations will be established before the study database is locked.

Completed Cases: The Completed Cases population is a subset of the Per-Protocol population and includes all patients who received the target treatment, do not have any major eligibility violations, and maintained stable glucose-lowering medications for 24 weeks post-procedure, and completed the final Week 48 End of Study Visit.

The details contained in this plan include the source code for the assessment of poolability across a myriad of factors and the analysis of each of the endpoints. Additionally, the structure of the table designs and a comprehensive index of the tables and listings has been provided.

This document contains information to support the generation of a Clinical Study Report (CSR). The planned analyses identified in this SAP may be included in regulatory submissions, medical presentations, and manuscripts. Exploratory analyses, not identified in this SAP, may be performed to support the clinical development program. Any post-hoc or unplanned analyses that are performed, but not identified in this SAP, will be clearly identified in the final report of the results. The structure and content of this SAP are designed to meet the requirements identified by the FDA and the International Conference on Harmonization (ICH) Guidance on Statistical Principles for Clinical Trials.

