The *Level 3* display will be used for summarizing the parameters recorded multiple times during the follow-up visits. An example of the layout is presented below; rows will be repeated for all visits where a measurement is recorded using the expanded time windows.

Level 3a Display

Parameter and Statistic	Observation Time	Device Generation 1 / 600 Volts / Single Treatment	Device Generation 1 / 600 Volts / Double Treatment	Device Generation 2 / 750 Volts / Double Treatment	All Patients
HbA1c	Baseline				
HbA1c	Post-Procedure Visit xxx				
HbA1c	Change from Baseline				

Level 3b Display

Parameter and Statistic	Observation Time	Device Generation 1 / 600 Volts / Single Treatment	Device Generation 1 / 600 Volts / Double Treatment and Device Generation 2 / 750 Volts / Double Treatment	All Patients
HbA1c	Baseline			
HbA1c	Post-Procedure Visit xxx			
HbA1c	Change from Baseline			

There will be 2 sets of comparative analyses prepared, each predicated on different combinations of device generation, voltage, and single vs. double treatment. The planned comparisons are outlined below.

Comparison Set 1

Device Generation 1 / 600 Volts / Single Treatment vs.

Device Generation 1 / 600 Volts / Double Treatment vs.

Device Generation 2 / 750 Volts / Double Treatment

Comparison Set 2

Device Generation 1 / 600 Volts / Single Treatment vs.

Device Generation 1 / 600 Volts / Double Treatment plus Device Generation 2 / 750 Volts / Double Treatment

Supportive individual patient data Listings will be sorted and presented by site number, patient number and visit date, if applicable. Listings will also include the number of days relative to the DMR index procedure. Specific algorithms are discussed for imputing missing or partially missing data, if deemed appropriate, under specific data topics. Imputed or derived data will be flagged in the individual patient data Listings. Imputed data, restricted to dates, will not be incorporated into any raw or primary datasets from the electronic capture system. The imputed data will be retained in the derived / analysis datasets.

Summary statistics will consist of the number and percentage of responses or counts at each level for categorical variables (e.g. race). For continuous variables, and the sample size (n), mean, median, standard deviation (SD), minimum, and maximum values will be presented.

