7.2. Adjustments for Covariates and Stratification Factors

Data will be presented by individual subgroups if there are a sufficient number of patients to warrant the breakdown. There are no planned stratification factors to be included in the models of the 5 different Comparison Sets.

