9.1. Analysis of the Primary Safety Endpoint

Each table number and population will clearly state; results will be presented using the Table 1a design. Results will be tabulated based on the number of patients experiencing one or more device-related or procedure-related serious adverse events at 12 weeks post-procedure.

The statement of the primary research question that will be addressed is as follows:

What percentage of the patients in the ITT population experienced one or more device-related or procedure-related serious adverse events within 12 weeks (84 days) of the index study procedure?

The statement of the secondary research question is specific below:

Is there a difference in the percentage of patients in the ITT population who experienced one or more device-related or procedure-related serious adverse events within 12 weeks (84 days) of the index study procedure based on the generation of the device, voltage, and single vs. double treatment?

The following model will be used to compare the groups identified within each Comparison Set. The dependent variable is the classification of each patient relative to experiencing a device-related or procedure-related serious adverse events at within 12 weeks (84 days) of the index study procedure [variable: DRPRSAE]. Contrast statements will be used to derive the estimates for each pair-wise comparison of a group.

```
PROC GLIMMIX DATA=COMP_SET_1 ;
  CLASS COMP_SET_1_GROUP;
  MODEL DRPRSAE = COMP_SET_1_GROUP / DIST=BINARY LINK=LOGIT
  SOLUTION;
  RANDOM INTERCEPT / SUBJECT=SUBJID_N ;
  LSMEANS TRTAN / DIFF CL;
RUN;
```

Sensitivity analyses will be performed using the FAS and PP populations. Results will be presented in the analysis table 14.4.1 entitled *Summary of the Device-Related or Procedure-Related Serious Adverse Events Within 12 weeks (84 days) of the index study procedure (ITT Population)* and table 14.4.1.1 entitled *Summary of the Device-Related or Procedure-Related Serious Adverse Events Within 12 weeks (84 days) of the index study procedure (FAS Population)* and table 14.4.1.2 entitled *Summary of the Device-Related or Procedure-Related Serious Adverse Events Within 12 weeks (84 days) of the index study procedure (PP Population)*. Listing 16.4.11 entitled *Adverse Events* provides supportive data for Tables 14.4.1, 14.4.1.1, and 14.4.1.2 will be sorted by site number and patient number.

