For each endpoint measured on a continuous scale, is there a difference in the estimates in the FAS population based on the generation of the device, voltage, and single vs. double treatment assessed over time?

The list of the top-line tables to be generated are presented below:

Table 14.4.1 entitled *Overall Summary of Procedure Success and Procedure Time (FAS Population)*

Table 14.4.2 entitled *Overall Summary of HbA1C, Fasting plasma glucose (FPG), Insulin-resistance by HOMA-IR, and Post-prandial plasma glucose (PPG) by Visit (FAS Population)*

Table 14.4.3 entitled *Overall Summary of Beta Cell Function by Visit (FAS Population)*

Table 14.4.4 entitled *Overall Summary of HbA1c improvement ≥ 0.3 points by Visit (FAS Population)*

Table 14.4.5 entitled *Overall Summary of Percent Change in Body Weight by Visit (FAS Population)*

Table 14.4.6 entitled *Overall Summary of Glucose-Lowering Medications by Visit (FAS Population)*

Table 14.4.7 entitled *Overall Summary of Liver Enzymes and Lipids by Visit (FAS Population)*

Table 14.4.8 entitled *Overall Summary of Blood Pressure Measurements by Visit (FAS Population)*

Table 14.4.9 entitled *Overall Summary of Continuous Glucose Monitoring (CGM) by Visit (FAS Population)*

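### The SAP plans mixed-model group comparisons of change from baseline without stating the model terms; if baseline is left out, any between-group baseline difference enters the contrasts

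*SAP*

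**What the plan says.** For HbA1c, SAP section 4.2.1 gives the endpoint as "Change from baseline (post-baseline minus baseline) in HbA1c reported for each pre-specified study visit" and adds: "The estimates will be derived using a mixed model repeated measure procedure; the 24 week result will be the principal time point of interest". Fasting glucose and HOMA-IR are worded alike. The meal-test measures also use a mixed model, with week 12 as the main time point.

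On group comparisons, SAP section 7 states: "There will be 2 sets of comparative analyses prepared, each predicated on different combinations of device generation, voltage, and single vs. double treatment". Set 1 compares three groups; set 2 compares single treatment with the two double-treatment groups pooled. The table in SAP section 3 gives 3, 7 and 10 patients, so set 2 is 3 against 17. For the repeated continuous endpoints, section 9.2 asks: "is there a difference in the estimates in the FAS population based on the generation of the device, voltage, and single vs. double treatment".

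On model content, section 7.2 is headed as covering covariates and stratification factors. It names no covariate and says: "There are no planned stratification factors to be included in the models of the 5 different Comparison Sets". Section 7 defines only two such sets. The introduction says "The details contained in this plan include the source code for the assessment of poolability" and goes on to promise code for the analysis of each endpoint. The only code shown is in section 9.1, for the binary safety endpoint: "MODEL DRPRSAE = COMP_SET_1_GROUP / DIST=BINARY LINK=LOGIT". Section 9.2 contains research questions and table titles, but no mixed-model code, terms or covariance structure.

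**The concern.** A change score is normally negatively related to its own baseline: patients who start higher tend to fall further. The groups here were not randomised. SAP section 5.1 assigns the first 10 patients to 600 V and the next 10 to 750 V, and nothing balances baseline HbA1c between them. With groups this small, a sizeable baseline difference can arise by chance alone. If the model leaves baseline out, part of that difference will appear as a difference between device settings. The estimate will also be less precise than the data allow. Because the terms are not written down, the choice could be made after the data have been seen.

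**Working it through.** There is no planned figure to reproduce. The tabulated 3 + 7 + 10 = 20 agrees with SAP section 5.3, which says that power calculations are not relevant.

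**Inputs**
- Group sizes: 3, 7 and 10 (SAP section 3), and 3 against 17 for set 2.
- SD of baseline HbA1c: σ = 0.9 points, from the 27 Australian patients described in Protocol Appendix 4, section 1. Using it for the SAP's 20 patients, and for follow-up as well as baseline, is an assumption.
- Baseline-to-follow-up correlation r: not in the documents; assumed 0.3 to 0.7.

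**Shift for a given imbalance.** With equal SDs, the slope of change on baseline is −(1 − r). A group starting D points higher therefore shows an extra fall of (1 − r)D with no difference in effect. For D = 0.5:
- r = 0.3: 0.7 × 0.5 = 0.35
- r = 0.5: 0.5 × 0.5 = 0.25
- r = 0.6: 0.4 × 0.5 = 0.20

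**Is D = 0.5 plausible?** The SD of a chance baseline difference is σ√(1/n₁ + 1/n₂). For 3 against 17 this is 0.9 × √(1/3 + 1/17) = 0.56. The probability column comes from a normal distribution for D.

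| Contrast | SD of D | Shift for a 1-SD imbalance (r = 0.3 / 0.5 / 0.7) | Probability that the shift exceeds 0.3 points |
|---|---|---|---|
| 3 vs 7 | 0.62 | 0.43 / 0.31 / 0.19 | 49% / 33% / 11% |
| 3 vs 10 | 0.59 | 0.41 / 0.30 / 0.18 | 47% / 31% / 9% |
| 7 vs 10 | 0.44 | 0.31 / 0.22 / 0.13 | 33% / 18% / 2% |
| 3 vs 17 | 0.56 | 0.39 / 0.28 / 0.17 | 45% / 29% / 8% |

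For scale, the responder cut-offs in the SAP are 0.3 and 0.5 points.

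**Precision.** In large samples the variance of the change contrast is proportional to 2(1 − r), and that of the adjusted contrast to 1 − r². The ratio is (1 + r)/2. At n = 20 the slope must be estimated, so the gain is smaller. I simulated 20,000 trials per setting with no true group difference, at one follow-up visit. The ratios of simulated variances, adjusted to unadjusted, were:

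| | r = 0.3 | r = 0.5 | r = 0.7 |
|---|---|---|---|
| Large-sample formula | 0.65 | 0.75 | 0.85 |
| 3 vs 17 | 0.69 | 0.79 | 0.91 |
| 7 vs 10 | 0.70 | 0.81 | 0.91 |
| 3 vs 7 | 0.76 | 0.87 | 0.99 |

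The slope of the unadjusted contrast on D was about −0.70, −0.50 and −0.30 for the three values of r. After adjustment it was about zero. Averaged over all possible imbalances, both contrasts had mean close to zero.

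**The case against.** The strongest reply is that the SAP is silent, and silence is not a specification. A reader might infer that the models exclude baseline, but the documents do not say so. Section 4.2.1 names a procedure without terms, section 7.2 rules out only stratification factors, and the one model statement belongs to a different endpoint. Section 9.2 asks about group differences without naming a model, so linking the mixed model to the contrasts is itself a reading, though the natural one. The SAP also refers to a parent protocol (Doc. No. 346) that is not among the documents and might state the terms. All of this stands, and it is why the shift is put conditionally.

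A reader might also infer that regression to the mean in general contaminates the contrasts. It does not: the part common to all groups cancels. It does remain in the overall single-arm change, where a baseline covariate would not remove it. Nor is the unadjusted contrast biased on average under chance imbalance; the shift is conditional on the imbalance observed.

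If the groups differ systematically, baseline adjustment is not automatically right, because it assumes one source population. Only the voltage sequence is documented; the SAP does not say how the 600 V patients divided into 3 single and 7 double treatments. Adjustment cannot separate device generation from voltage, or either from calendar time.

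Finally, the stakes are limited. SAP section 7.1 calls the testing informative only, section 9 says there are no formal hypothesis tests, and the Level 3 displays show each group's baseline beside its change, so an imbalance would be visible. These points limit the consequence but do not supply the missing model.

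**Conclusion.** The point holds as a gap in specification with a calculable consequence. The SAP plans group contrasts of change scores, states no mixed-model terms and plans no baseline covariate, despite promising code for each endpoint. If baseline is omitted, a 0.5-point HbA1c imbalance, which is ordinary for groups of this size, shifts the contrast by 0.20 to 0.35 points for r between 0.6 and 0.3.

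A reader might take the large-sample reduction in variance, 35% at r = 0.3 and 20% at r = 0.6, as the expected gain. At these group sizes it is less: about 31% at r = 0.3 and 9% at r = 0.7 for 3 against 17, and almost nothing at r = 0.7 for 3 against 7. These sizes rest on an assumed r, a proxy SD of 0.9, equal SDs at both times and a common source population. Because the comparisons are secondary and informative, this is a desirable improvement that does not affect the primary safety result.

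**What to change.** In SAP sections 7.2 and 9.2, write the model out: change = group + visit + group-by-visit + baseline value of the same measure. Add baseline-by-visit only if it can be estimated with 20 patients; over the five HbA1c visits it needs four further parameters. Specify Kenward-Roger degrees of freedom and name in advance a simpler covariance structure, such as compound symmetry, to use if the unstructured form does not converge. Correct the count of Comparison Sets in section 7.2 to match section 7.

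State alongside the results that the adjusted contrasts assume a common source population, do not remove confounding by device generation, voltage or calendar time, and remain descriptive.

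The cost is a paragraph of SAP text and one to a few degrees of freedom. No new data are needed, since SAP section 7 already defines the pre-procedure baseline.

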A subsequent study⁹ enrolled 46 patients, among them 37 completed the DMR procedure. Patients were 31-69 years old, 63% of them were male, had a mean BMI of 31.6 kg/cm² and a baseline HbA1C of 8.6%. Improvements in HbA1c, FPG and HOMA-IR levels were observed as early as 4 weeks and sustained out to 12 months. Mean HbA1C reduction was 0.9% at 24 weeks, which was preserved up to 12 months. HOMA-IR was reduced by 2.9±1.1 at 24 weeks and by 3.3±0.9 at 12 months from baseline. The study also observed a statistically significant decrease in alanine transaminase (ALT) levels at 24 weeks and 12 months post procedure. Patients had a modest weight loss of 2.5kg at 24 weeks and 2.4 kg at 12 months. Most common study-related adverse events were GI symptoms. One study-related serious adverse event involved a patient with general malaise, mild fever (38°C), and increased c-reactive protein (CRP) level on the first day after DMR. The mild fever resolved within 24 hours and CRP level normalized within 3 days. No stenosis was reported in this study.

The above data supports the hypothesis that interventions targeting duodenal mucosa can improve glycemic control in T2D patients inadequately controlled by OAD. One limitation of hydrothermal ablation is the need to inject saline into the submucosal layer (mucosal lifting) during the ablation procedure for the purpose of preventing thermal penetration into deeper tissue. In addition to technical demand, mucosal lifting potentially creates irregular contacting surface between the ablation balloon and mucosa, resulting in uncontrolled and nonuniform ablation. One potential solution to address this limitation is to use an regeneration technology that does not require mucosal lifting.

Endogenex has developed a duodenal mucosal treatment device using a pulsed electric field (PEF) with bipolar pulse technology for the treatment of T2D. The treatment does not require mucosal lifting to protect muscularis from thermal damage, and therefore results in a simpler procedure and potentially more uniform tissue treatment.

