3 STUDY OBJECTIVES AND ENDPOINTS

The objective of this first-in-human study is to assess the feasibility and preliminary safety of the Endogenex device for endoscopic duodenal mucosal regeneration in individuals with type 2 diabetes inadequately controlled on glucose-lowering medications.

The study will also assess, as exploratory endpoints, treatment efficacy, evaluated by changes in glycemic control and liver enzymes post procedure from baseline.

Objectives	Endpoints
Primary 
 • To assess the safety of the Endogenex device for DMR procedure 	
 • Proportion of participants experiencing one or more device- or procedure-related serious adverse events at 12 weeks post procedure.
Secondary 
 • To assess the technical feasibility of the Endogenex device for DMR procedure • To assess changes in glycemic control • To assess changes in liver enzymes 	
 • Procedure success: defined as successful treatment of at least 6 cm of duodenum segment. • Procedure time: defined as the time between the Endogenex catheter insertion and the catheter removal. • Change from baseline in glycemic parameters post index procedure, by visits 
 ○ HbA1c ○ Fasting plasma glucose (FPG) ○ Insulin-resistance by HOMA-IR ○ Post prandial plasma glucose (PPG), Beta cell function, disposition index by mixed meal tolerance test (MMTT) • Proportion of treated participants with an HbA1c improvement of 0.3% or more at 24 weeks from baseline • Proportion of treated participants with an HbA1c improvement of 0.3% or more at 24 weeks from baseline and maintained at 48 weeks • Change in weight from baseline by visit • Change in glucose-lowering medication usage • Change in liver enzyme from baseline at 24 weeks 
 ○ Alanine Aminotransferase (ALT) ○ Aspartate Aminotransferase (AST) • Change from baseline in blood pressure and lipid profile by visit

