5.3. Sample Size Justification

The study plans to enroll 20 participants and test two treatment parameters (600 volts and 750 volts), with 10 participants treated in each group. As this study is intended to characterize device safety and feasibility outcomes, formal sample size and power calculations based on hypothesis testing against a priori statistical objectives are not relevant; a sample size of 10 in each group and 20 in total is considered to be sufficient for the objectives of this investigation.

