Proportion of treated patients with an HbA1c improvement of $\geq 0.5\%$ from baseline at 24 weeks (24 week score minus baseline score). Patients who fail to have HbA1c improvement of ≥ 0.5 points from baseline, for any reason, will be counted as not having achieved this endpoint.

Ninth Secondary Endpoint

The distribution of this endpoint is binary. Proportion of treated patients who achieve a HbA1c improvement of $\geq 0.5\%$ or more at 24 weeks from baseline and maintained at 48 weeks. Patients who fail to maintain HbA1c improvement $\geq 0.3\%$ at 48 weeks, for any reason, will be counted as not having achieved this endpoint. Patients who fail to achieve a HbA1c $\geq 0.5\%$ at 24 weeks will be excluded from the tabulation. The primary population for analysis of this endpoint will be the FAS population.

Proportion of treated patients with an HbA1c improvement $\geq 0.5\%$ from baseline at 24 weeks maintained at 48 weeks.

Tenth Secondary Endpoint: The distribution of this endpoint is continuous. The primary population for analysis of this endpoint will be the FAS population. Change in weight from baseline (post-baseline minus baseline) by visit. Weight change will be reported in both kilograms and %TBWL.

Eleventh Secondary Endpoint: Change in glucose-lowering medication usage.

Twelfth Secondary Endpoint: The distribution of this endpoint is continuous. The primary population for analysis of this endpoint will be the FAS population. Change in liver enzyme from baseline at 24 weeks (post-baseline minus baseline) for Alanine Aminotransferase (ALT).

Thirteenth Secondary Endpoint: The distribution of this endpoint is continuous. The primary population for analysis of this endpoint will be the FAS population. Change in liver enzyme from baseline at 24 weeks (post-baseline minus baseline) for Aspartate Aminotransferase (AST).

Fourteenth Secondary Endpoint: The distribution of this endpoint is continuous. The primary population for analysis of this endpoint will be the FAS population. Change from baseline in blood pressure by visit (systolic and diastolic run separately).

Fifteenth Secondary Endpoint: The distribution of this endpoint is continuous. The primary population for analysis of this endpoint will be the FAS population. Change in lipid profile from baseline by visit: total cholesterol

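### SAP eighth secondary endpoint (Week-24 HbA1c responder): the stated difference has the wrong sign for an improvement, and the threshold is 0.5 in the endpoint text but 0.3 in the table title

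*SAP*

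**What the plan says.** **Endpoint text in the SAP.** The eighth secondary endpoint is the proportion of treated patients whose HbA1c improves by at least 0.5 at Week 24. It appears in three places, each with a bracket that states how the difference is formed:

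- SAP 4.2.1: "points from baseline at 24 weeks (24 week value minus the baseline value").
- SAP 9: "from baseline at 24 weeks (24 week score minus baseline score"). The operative rule follows: "Patients who fail to have HbA1c improvement of ≥ 0.5 points from baseline, for any reason, will be counted as not having achieved this endpoint".
- SAP 9.2, list of binary endpoints: the same 0.5 and the same bracket as SAP 9.

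**Table in the SAP.** The list of top-line tables at the end of SAP 9.2 has one table on HbA1c response, Table 14.4.4: "Overall Summary of HbA1c improvement ≥ 0.3 points by Visit (FAS Population").

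**Supplied protocol (No. 196).** Section 3 has "Proportion of treated participants with an HbA1c improvement of 0.3% or more at 24 weeks from baseline". The Protocol Summary and Table 1 of Appendix 4 also use 0.3.

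**Which protocol the SAP serves.** SAP 3 says it covers the REGENT-1-US study, Doc. No. 346. It gives no reason for using 0.5.

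**The concern.** There are two defects, and they are independent of each other.

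The first is the sign. Improvement in HbA1c means a fall. A fall makes Week 24 minus baseline negative, so it can never reach +0.5. The SAP also uses post-procedure minus baseline as its general change score (SAP 7) and for the HbA1c change endpoint (SAP 4.2.1). A programmer is therefore likely to have exactly that variable to hand. If it is tested against 0.5 as the bracket suggests, the reported success rate is a deterioration rate. The only model code shown, in SAP 9.1, is for the primary endpoint, so no code settles the direction.

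The second is the threshold. If the endpoint is programmed from the text and the table from its title, one report carries two responder definitions. The ninth endpoint (response maintained at 48 weeks) excludes patients who miss the Week-24 criterion, so the eighth endpoint's definition also determines the ninth's denominator. The ninth mixes 0.3 and 0.5 as well: SAP 4.2.1 puts a 0.3 at Week 24, and SAP 9 puts it at Week 48.

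**Working it through.** The documents give no power, alpha or expected rate for this endpoint. SAP 5.3 says only that "a sample size of 10 in each group and 20 in total is considered to be sufficient for the objectives of this investigation". There is thus no planned figure to reproduce. The check compares the texts, then works through examples and an illustration of size.

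**1. Sign, worked cases.** Start from 8.6%, the mean baseline that Protocol Appendix 4 reports for the first 27 treated patients. Let D = Week 24 − baseline ("24 week score minus baseline score"), with the literal rule D ≥ 0.5.

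- 8.6 to 7.6: D = −1.0. Improved by a full point, not counted.
- 8.6 to 9.2: D = +0.6. Worsened, counted.

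With the difference reversed (baseline − Week 24), the values are +1.0 (counted) and −0.6 (not counted), as intended.

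**2. Threshold, worked case.** 8.6 to 8.2 is a fall of 0.4. This patient is a responder at 0.3 and a non-responder at 0.5.

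**3. Side by side.**

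| Place | Threshold | Stated difference |
|---|---|---|
| SAP 4.2.1, eighth endpoint | 0.5 | Week 24 − baseline |
| SAP 9, eighth endpoint | 0.5 | Week 24 − baseline |
| SAP 9.2, binary endpoints | 0.5 | Week 24 − baseline |
| SAP 9.2, Table 14.4.4 title | 0.3 | none |
| Protocol No. 196, Summary, Section 3, Appendix 4 | 0.3 | none |

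**4. Size, for illustration.** Assume the Week-24 fall is normal with mean 0.9 and standard deviation s. The mean comes from Protocol 1.2, which reports for a hydrothermal device: "Mean HbA1C reduction was 0.9% at 24 weeks, which was preserved up to 12 months". It is not a forecast for this device. The documents give no SD of change, so s = 0.8 to 1.2 is an assumption.

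- P(fall ≥ 0.3) = Φ((0.9 − 0.3)/s)
- P(fall ≥ 0.5) = Φ((0.9 − 0.5)/s)
- P(rise ≥ 0.5) = 1 − Φ((0.9 + 0.5)/s)

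| s | fall ≥ 0.3 | fall ≥ 0.5 | literal rule (rise ≥ 0.5) |
|---|---|---|---|
| 0.8 | Φ(0.75) = 77% | Φ(0.50) = 69% | 1 − Φ(1.75) = 4% |
| 1.0 | Φ(0.60) = 73% | Φ(0.40) = 66% | 1 − Φ(1.40) = 8% |
| 1.2 | Φ(0.50) = 69% | Φ(0.33) = 63% | 1 − Φ(1.17) = 12% |

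With 20 patients and s = 1.0, the expected counts are 14.5, 13.1 and 1.6. The choice between thresholds moves about 1.4 patients. The sign changes what is being counted.

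**5. Sensitivity.** Over mean falls of 0.5, 0.9 and 1.2 and SDs of 0.8 to 1.3, moving from 0.5 to 0.3 raises the rate by 5 to 10 percentage points, or 1 to 2 of 20 patients. The literal rule gives 2–22%, against 50–81% for a true fall of at least 0.5.

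**The case against.** **The intent is plain.** All three SAP texts say improvement, and the rule in SAP 9 that assigns failures carries no sign: a patient whose HbA1c rises fails it. The bracket looks like a carry-over of the general change-score convention. This stands. A reader might infer that the SAP means to report worsening as success, and the documents do not support that. The 4–12% describes a coding error that the wording permits, not a planned analysis.

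**The threshold mismatch does not cause the sign problem.** This also stands. Worsened patients would be counted because of the sign alone, whichever threshold is used.

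**The parent protocol may be a different document.** SAP 5.1 describes a US study of 20 participants on 2–3 medications with baseline within 21 days. The supplied protocol describes an Australian study with 1–4 medications, 28 days and up to 60 non-insulin participants. SAP 3, however, also says Australia, so the identity is unclear. Document No. 346 might specify 0.5. It follows that 0.3 is not shown to be the pre-specified threshold for this SAP. The conflict inside the SAP between 0.5 and the Table 14.4.4 title does not depend on this.

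**A late change is not shown.** A reader might infer from the patient counts in SAP 3 (3, 7 and 10) that the threshold was changed after treatment in an open-label study. The counts suggest that at least some patients had been treated. Nothing dates the choice of 0.5 or shows that HbA1c results had been seen, and 0.5 is the stricter cut.

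**Little depends on it.** This is one of 18 secondary endpoints. SAP 7.1 calls any testing informative only, HbA1c change is reported at each HbA1c visit, and all data are listed, so either cut can be recovered. That limits the severity but does not make the rule usable as written.

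**Conclusion.** The concern holds as two separate wording defects in the eighth secondary endpoint. First, the stated difference has the wrong sign for an improvement in SAP 4.2.1, 9 and 9.2, although the intended direction is clear. Second, the threshold is 0.5 in those three places and 0.3 in the title of Table 14.4.4 and in the supplied protocol. Which threshold governs cannot be settled without the protocol that the SAP names.

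The textual findings need no assumptions. The sizes depend on a normal model, a mean borrowed from another device and an assumed SD, and serve only to show scale: the threshold matters by roughly 1 to 2 of 20 patients, while a literal coding of the sign would make the result meaningless. The primary safety endpoint and the sample size are unaffected. Severity: should fix, before the endpoint is programmed.

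**What to change.** 1. In SAP 4.2.1, 9 and 9.2, define response as baseline minus Week-24 HbA1c at or above the threshold. Equivalently, keep the SAP's change score and require it to be at or below minus the threshold.
2. Use one threshold in those three places and in Table 14.4.4, reconciled with the governing protocol. If that protocol says 0.3, keep 0.3 as the endpoint and report 0.5 as a labelled supplementary cut. If 0.5 is kept, cite its source and label any departure from the protocol.
3. Keep Table 14.4.4 by visit, with Week 24 and Week 48 under the same definition. Restricting it to Week 24 would leave the 48-week maintenance endpoint without a listed responder table.
4. Carry the settled Week-24 definition into the ninth endpoint, whose denominator depends on it.

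The cost is SAP wording and one table title. No data collection, visit or sample size changes.
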